The anatomical laboratory provides a controlled environment, ideal for simulating surgical procedures, allowing the analysis of multiple variables that influence the effectiveness of the procedure and cannot be controlled in clinical practice (4–14). Recently, the Principal Investigator (PI) developed, in collaboration with the University of Toronto, a navigation system that allows for the quantification of the workspace to define a specific surgical approach (14–19). This new method has been used in several anatomy laboratories, including those at the Universities of Brescia, Toronto, and Geneva, to conduct comparative quantitative studies on various neurosurgical, otolaryngological, and skull base surgery approaches. Some of the results obtained have been published in international scientific journals (14–24).

Objective

The main objective of this study is to conduct a preclinical and systematic analysis of the various cranial and spinal surgical approaches to evaluate their potential and limitations in an objective manner. Attention will be particularly focused on the study of skull base approaches, spinal approaches, quantitative studies, exploration of anatomical variations, and the validation of new surgical approaches and related instruments.

Endpoints

Primary Endpoints:

1. Quantification of Work Volume and Exposed Area in Crano-Spinal Surgical Approaches

Work volume represents the three-dimensional operative space created by each crano-spinal surgical approach. Quantification will be performed using BrainChop imaging software on standardized CT scans. Segmentation will follow predefined protocols to ensure reproducibility. Higher values indicate a larger and more accessible operative corridor. Exposed area corresponds to the two-dimensional anatomical surface revealed by each surgical approach. Measurements will be obtained from CT-based reconstructions using the same standardized segmentation workflow. Higher surface values reflect wider surgical exposure.

Unit of Measure: cubic millimeters (mm³) and square millimeter.

Time Frame: Measurements will be obtained twice with BrainChop software for each approach on every specimen: before the dissection using baseline CT imaging and after completing the approach using repeat CT imaging on the same day.

Secondary Endpoints:

1. Analysis of anatomical variations influencing surgical approaches.
2. Validation of new surgical instruments and techniques on cadaveric specimens.

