- **Third Year:** The focus will be on macroscopically and microscopically visualized skull base and spinal approaches. Quantitative analyses will be conducted, relevant anatomical variations will be explored, and new surgical approaches and related instruments will be validated.

Setting

The anatomical dissections will be performed at the SURGEM Laboratory (located in the Settorian Room of the Institute of Pathological Anatomy at the Catholic University of the Sacred Heart in Rome). Recruitment of specimens began on 15/10/2025 and will continue throughout the study, which is expected to last for three years. The dissections, data collection, and analysis will be carried out continuously during this period.

Procedure

The anatomical specimens will be sourced from the Catholic University of the Sacred Heart's voluntary donation program and the Science Care Program. Sixty percent of the specimens will undergo specific preparations, including arterial and/or venous injections with silicone, consisting of a base and catalyst (Xiameter®, Midland, MI, USA) and colored with Pintasol® (Mixol® Red E-L3mix, Kirchheim unter Teck, Germany). The specimens will undergo high-resolution CT scans, and the DICOM images will be imported into a dedicated neuronavigation system (GTx-Eyes II Approach Viewer, University Health Network, University of Toronto, Toronto, Ontario, Canada). In some cases, CT scans will be repeated after dissection, and new calculations will be made using the neuronavigation software.

CT scans will be performed at the Institute of Forensic Medicine at the Catholic University of the Sacred Heart. The source of the specimens will be tracked and recorded, including:

- Voluntary donation program at the Catholic University of the Sacred Heart, Rome, Italy, in accordance with Italian law (LAW 10 February 2020, No. 10 and DECREE OF THE PRESIDENT OF THE REPUBLIC 10 February 2023, No. 47);
- Science Care, USA.

The dissections will be performed using neuro-surgical instruments specific for skull base surgery available at the SURGEM laboratory:

- Complete set of Rhoton dissectors (Rhodon Micro Dissector).
- Complete set for skull base surgery (Karl Storz®, Germany).

- Zeiss microscope (UCSC 119473).

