The specimens will be cataloged according to their source, and anonymized data provided by the donor centers will be entered into a database. Proper storage of the specimens will take place at the Institute of Pathological Anatomy (Head: [name]) at the Catholic University of the Sacred Heart. Non-fixed specimens will be stored frozen at -20°C in dedicated freezers, while fixed specimens (with formalin) will be stored at 4°C in a solution (formaldehyde, glycerol, alcohol reagent, and water).

Variables

The approaches will be performed in a modular manner, from the least invasive to the most extensive. Various surgical approaches will be simulated using surgical instruments dedicated to skull base surgery, spinal surgery, and in both macrosurgical and microsurgical visualization modes.

The quantification of the working volume and the exposed area for each surgical approach will be calculated with an open-source software (BrainChop) on the CT scans of the specimens obtained before and after surgical dissection. For each specimen's CT scan, the area of interest exposed by the different approaches to be compared will be outlined using the BrainChop software (14-24).

Error and Control

To minimize potential sources of error, rigorous control methodologies will be implemented during data collection. Each analysis will be repeated multiple times to ensure the accuracy of the results.

Sample Definition

Given the descriptive nature of the study, a formal sample size determination is not required. However, we estimate that 35 cadavers will be enrolled over the three-year period.

Statistical Analysis

Quantitative variables will be summarized as means and standard deviations, while qualitative variables will be reported as absolute and relative frequencies (percentages). The effectiveness of the training will be evaluated by testing the mean difference of scores obtained in tests administered before and after the training, using the paired Student's t-test or the Wilcoxon test.

The difference in execution times between different techniques will be tested using ANOVA or the Kruskal-Wallis test. Linear models with random intercepts will be used to compare surgical volumes and exposed areas. A 95% confidence interval will be estimated using the bootstrap resampling method.

Results with $p < 0.05$ will be considered statistically significant. Statistical analysis will be performed using STATA software (StataCorp® LLC, College Station, TX, USA).

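### Do the random-intercept model and a bootstrap with no stated resampling unit make the intervals for volume and area too narrow?

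*Protocol*

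**What the plan says.** Under Primary Endpoints (Time Frame), the protocol states: "Measurements will be obtained twice with BrainChop software for each approach on every specimen". One measurement uses the CT before dissection, which the protocol calls the baseline, and the other uses the CT after the approach is completed. Under Error and Control, as a safeguard against measurement error, it adds: "Each analysis will be repeated multiple times to ensure the accuracy of the results".

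The Statistical Analysis section then gives two sentences on the primary endpoint: "Linear models with random intercepts will be used to compare surgical volumes and exposed areas" and "A 95% confidence interval will be estimated using the bootstrap resampling method". The threshold follows: "Results with $p < 0.05$ will be considered statistically significant".

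Under Sample Definition the study is called descriptive, "a formal sample size determination is not required", and "we estimate that 35 cadavers will be enrolled over the three-year period".

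The protocol does not state the level at which the intercepts enter, the unit that is resampled, the number of repeats, or whether repeats are averaged before modelling. It also does not say how the baseline value is used.

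**The concern.** The data have layers: cadaver, approach within cadaver, and repeat or time point within approach. A model with one intercept per cadaver treats two readings of the same approach in the same cadaver as independent once the cadaver is accounted for. They are not independent if that cadaver's anatomy makes that approach roomier or tighter than average. Re-segmenting one CT would then count almost like adding a cadaver. A bootstrap that draws single rows and refits that model would share the fault.

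The pre-dissection value adds a second worry. It does not result from any approach, and if it were pooled with the post-dissection value it would dilute the difference between approaches.

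If the plan worked this way, more repeats would mean narrower intervals for volume and area without more information, and false differences between approaches would be declared.

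**Working it through.** **Inputs.** From the protocol: S = 35 cadavers (a planning estimate), nominal level 95%. Assumed, because the protocol gives none: K = 3 approaches, all done on every cadaver; R = 1 to 5 repeats; variances for cadaver (Vu), cadaver-by-approach (Vv) and repeat (Ve) that sum to 1. The protocol has no interval width or SD to reproduce.

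**1. True variance of the difference between two approaches**

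2 (Vv + Ve/R) / S

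**2. Variance reported by a cadaver-only intercept with repeats as rows**

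2 s² / (S R), with expected s² = [(S−1)(K−1)(R Vv + Ve) + S K (R−1) Ve] / (S K R − S − (K−1))

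For Vv = 0.4, Ve = 0.1, R = 3:
- s² = [34 × 2 × 1.3 + 105 × 2 × 0.1] / 278 = 109.4 / 278 = 0.3935
- reported variance = 2 × 0.3935 / 105 = 0.00750
- true variance = 2 × (0.4 + 0.0333) / 35 = 0.02476
- SE ratio = √(0.00750 / 0.02476) = 0.55
- coverage = 2Φ(1.96 × 0.55) − 1 = 72%

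The mechanism is therefore real under these premises. The same formulas give this coverage for the cadaver-only model:

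| Vu / Vv / Ve | R = 1 | R = 2 | R = 3 | R = 5 |
|---|---|---|---|---|
| 0.5 / 0.4 / 0.1 | 95% | 82% | 72% | 60% |
| 0.5 / 0.25 / 0.25 | 95% | 87% | 80% | 70% |
| 0.2 / 0.7 / 0.1 | 95% | 80% | 70% | 57% |
| 0.8 / 0 / 0.2 | 95% | 95% | 95% | 95% |

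**3. Remove one premise at a time**
- *Repeats averaged.* This leaves one value per approach and cadaver with variance Vv + Ve/R around the cadaver level. The formula in step 2 with R = 1 then gives s² = Vv + Ve/R, so the SE ratio is 1.00 and coverage 95%. A simulation of 5000 replicates with averaged repeats gave 94% to 95%.
- *Intercepts for cadaver and for approach within cadaver.* The model variance is 2 (R Vv + Ve) / (S R) = 2 (Vv + Ve/R) / S, which is the true variance. For the example, 2 × 1.3 / 105 = 0.02476.
- *Little or no cadaver-by-approach variance.* With Vv = 0 the ratio is 1.00 for any R. With SDs of 0.1 (cadaver-by-approach) and 0.3 (repeat) and R = 3, s² = [68 × 0.12 + 210 × 0.09] / 278 = 0.0973. The ratio is √[(0.0973/3) / (0.01 + 0.03)] = 0.90, and coverage is 92%.

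**4. The bootstrap.** Suppose rows are resampled and raw means compared. The variance is then about 2 (Vu + Vv + Ve) / (S R), and the SE ratio is √[(1/R) / (Vv + Ve/R)]. With R = 1 this is √(1/0.8) = 1.12 to √(1/0.2) = 2.24, so intervals are too wide. With R = 3 it runs from 0.67 to 2.24 over the variances tried, so the error can go either way.

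If rows are resampled and the cadaver-only model is refitted with R = 3, simulated coverage was 71.5% and 80.5% for the first two table rows, and 97.5% for the last. Resampling whole cadavers gave 92%, 91.5% and 95%. These simulations used 200 runs, with a Monte Carlo error of 2 to 3 points.

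**5. The baseline value.** Let b be a baseline common to approaches A and B. Pooling pre and post rows with approach as the only factor gives (b + A)/2 − (b + B)/2 = (A − B)/2, so a difference of 50 becomes 25. Using the post value gives A − B = 50. Using the change gives (A − b) − (B − b) = 50. The protocol labels the first scan a baseline and defines work volume as the space an approach opens, and nothing in it calls for pooling.

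**The case for a change.** The strongest reply is that the wording permits the bad analysis and nothing rules it out. The protocol itself plans the repeats and the pre and post values, and its analysis sentences connect to neither. Zero cadaver-by-approach variance is also unlikely here, since anatomical variation that influences the approaches is a secondary endpoint. The choice between post value and change touches the definition of the primary endpoint, and a few sentences would settle all of it.

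Part of this stands. The data structure is described correctly, the arithmetic in step 2 is right, and more explicit text would be welcome. But a plan that allows a poor implementation has not chosen it. Random intercepts are a method for correlated readings, and an analyst who plans them already has the clustering in mind. Repeats listed as an error-control measure are most naturally averaged. One averaged value per approach, a cadaver intercept and resampling of whole cadavers would carry out the two existing sentences without contradicting either.

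A separate matter is that Procedure says "In some cases, CT scans will be repeated after dissection", which does not agree with the Time Frame wording. That affects how many post-dissection values exist. It does not show that the model or the bootstrap is wrong.

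**Conclusion.** The concern does not hold. The loss of coverage (about 57% to 87% with 2 to 5 repeats, in the table rows with cadaver-by-approach variance) needs three things together: repeats as separate rows, no intercept below cadaver level, and appreciable cadaver-by-approach variance. The protocol states neither of the first two, and the third is an assumption. Row-level resampling is not stated either, and its effect on interval width has no fixed direction. The halved difference needs a pooling of baseline and outcome that the protocol does not describe.

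The protocol names a suitable model class and a usable interval method, and leaves grouping level, resampling unit and the handling of repeats and baseline open. That is normal SAP content, and the SAP is not shown. The conclusion would change if the SAP fixed a cadaver-only intercept with repeats as rows and row-level resampling. All coverage figures rest on 3 assumed approaches, assumed repeat counts and assumed variances, and are not figures of this study.
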